Clinicaltrials.gov application number: NCT04110314

Title: *Improving Influenza Vaccination Delivery Across a Health System by the Electronic Health Records Patient Portal*

IRB ID17-001889, Amendment 10 for RCT2

Submission Date: 12/14/2017 (RCTs 1-5) **IRB Approval Date:** 12/20/2017

Amendment for RCT2: Approved 10/9/2019

Informed Consent form N/A (approved Waiver of Consent)

RCT2 Protocol (includes statistical analysis plan)

SPECIFIC AIMS

The overall purpose of the RCTs is to evaluate the impact that R/R, delivered through the patient portal, could have on the flu immunization rates of UCLA Health patients. The intent is to ultimately take the information learned and create and disseminate an adaptable toolkit to other health systems.

For RCT #2, we will evaluate the impact of positively framed messages versus negatively-framed messages versus control (standard of care) to see if either type of message has an impact on the receipt of influenza vaccination. The current literature is mixed as to which message type is more effective. The RCT #2 study design will enable us to evaluate the impact in different sub-populations which may demonstrate variability in preference. In addition, RCT #2 will allow us to test the impact of pre-commitment. In the field of behavioral economics, pre-commitment has shown promise as a means of behavior change- in this case, receipt of influenza vaccination. The study design will enable us to evaluate the impact of a pre-commitment question.

Specific Aims for RCT 2:

Aim 1 RCT #2: Using a 3-arm RCT (up to 55 practices), compare the effectiveness of flu reminder recall messages that have been tailored for one of 4 subpopulations- 1) children <18 years, 2) young adults (18-<65 years), 3) older adults (65+ years) and 4) patients with diabetes (identified by SUPREME criteria by CTSI). Within each subpopulation, one arm will receive positively-framed messages highlighting the benefits of flu vaccination, one arm will receive negatively framed messages highlighting the risks associated with not getting the flu vaccine and one arm will serve as the control arm (no portal reminders).

Aim 2 RCT #2: In addition, we will test the impact of a "pre-commitment" question asking whether the patient plans to receive the flu vaccine (prior to the reminders going out). This question will be asked of half of patients per arm of the 3-arm RCT. Previous research has indicated pre-commitment can improve the likelihood a patient follows through with a behavior. We intend to determine whether pre-commitment increases the likelihood of getting the flu vaccine.

In summary, families will be randomized using a 3x2 factorial allocation (no reminder v. positively-framed reminder v. negatively-framed reminder, and no pre-commitment question v. pre-commitment question). Family members will be divided into 4 non-overlapping cohorts (age <18 years, 18-64 years non-diabetic, 65+ years non-diabetic, and 18+ years diabetic), and a single index member per family per cohort will be selected for inclusion in the study. Only active users affiliated with a UCLA primary care practice will be included in the study sample. For single individuals not part of a family, that individual will serve as the index patient.

Hypotheses:

Hyp 1 RCT #2: Vaccination rates will differ by receipt of no reminders, positively framed reminders and negatively framed reminders.

1.1 Vaccination rates will be higher among patients receiving positively framed reminders than among patients receiving no reminders.

1.2 Vaccination rates will be higher among patients receiving negatively framed reminders than among patients

receiving no reminders.

1.3. Vaccination rates will be higher among patients receiving positively framed reminders than among patients receiving negatively framed reminders.

Hyp 2 RCT #2: Vaccination rates will be higher among patients receiving a pre-commitment question than among patients not receiving the pre-commitment question.

2.1 The arm receiving the pre-commitment question, asking about their intention to get the flu vaccine (prior to the reminders going out), are more likely to follow through with influenza vaccination; therefore, the pre-commitment arm will have higher rates of flu vaccination than the control arm for the pre-commitment component.

The RCT design, subpopulations and letter components have been approved by the MyChart subcommittee, Ambulatory Operations Advisory Group, and the UCLA Health Primary Care Committee.

METHODS AND STUDY PROCEDURES

The UCLA Health System is made up in part of approximately 55 primary care practices. The leadership team at UCLA Health has agreed to allow these practices to participate in the RCT.

Among the primary care practices (up to n= 55), patients who meet the inclusion criteria will be randomized into the study arms (no reminder v. positively-framed reminder v. negatively-framed reminder, and no pre-commitment question v. pre-commitment question).

Eligibility for R/R: Our EHR will identify subjects who are eligible for either 1 or 2 influenza vaccinations based on ACIP algorithms (2 are recommended for children <9 years who have not had a prior flu vaccination).

Spacing of R/R messages: Based on our prior studies, we plan to send up to 4 R/R messages, spaced every 3-4 weeks, beginning in October.

Languages: R/R messages will be in English. Portal messages in Spanish will not be available during RCT 2 due to technological capabilities.

Health Literacy: We will use plain language <7th grade reading level per Flesch-Kincaid analysis.

[figure not shown]
R/R Message Content: The content of each R/R message are slightly modified to be tailored to each age group/condition (diabetes). Please see item 10.0 of the IRB system for examples of the messages to be used (title: RCT #2 Reminders).

OVERALL STUDY DESIGN

Subjects receiving the intervention will be patients at one of the primary care practices within UCLA Health's System (up to 55 practices) and will include patients of any age greater than 6 months of age at the time of messages being sent. A proportion of the patients from these practices will be selected to participate - i.e., those who meet the inclusion criteria. Randomization techniques will occur before each RCT.

For RCT2, we are sending enhanced reminder/recall (R/R) messages. Specifically, UCLA portal users will be divided into 4 groups that will get tailored messages. These groups are: 1) parents of children <18 years of age, 2) adults ages 18-<65 years of age, 3) adults ages 65 or older and 4) individuals meeting the SUPREME diabetes criteria. Participants will be randomized to receiving positively-framed messages, negatively-framed messages or no portal messages regarding influenza vaccination. Participants will also be randomized to either receiving a pre-commitment prompt or no pre-commitment prompt.

Study Design for Pediatric, Young Adult and Older Adult and Diabetic Patient RCTs

* Messages emphasize the benefits of being vaccinated; ** Messages emphasize the risks of not getting vaccinated.

Subject Population

There are approximately n = 430,000 patients in the primary care registry (RCT#2) who are active/inactive portal users and affiliated with the primary care practices of interest for this research. And additional 50,000 meet the SUPREME criteria for diabetes.

Many patients are members of the same family. As such, the research team will assemble family units (using household address, primary telephone number, patient ID of the guarantor, and insurance member ID as the variables of commonality to create these family units). For RCT 2, for each family, 1 individual will be randomly selected as the index patient for each age or diabetic subgroup. Only index patients who are also active portal users and affiliated with a primary care practice (criteria explained below) will have their data analyzed as part of the primary analysis plan.

Secondary analyses will involve all study subjects.

Gender and age: We anticipate the gender distribution to be roughly equal. All ages of patients will be included in the study; however, patient will not receive a message until they are 6 months of age, as the flu vaccine is not recommended for those less than 6 months of age.

Racial and ethnic origin: There are no enrollment restrictions based on race/ethnicity.

Inclusion criteria

A patient at one of the clinics of interest within the UCLA Health System (up to 55 practices). An individual is deemed a primary care patient of the UCLA Health System through the following algorithm:

Assigned managed care patients (UCLAMG) + Attributed patients from other payers/ACOs

≥2 PCP visits in the past 3 years; or

≥1 PCP visit with preventive service code in past 1 year (99381-99397 or G0438/G0439)

All visits cannot be urgent care visits (i.e., excludes visits after hours or on weekends, not by urgent care codes since UCLA does not bill accordingly)

Active patient: We decided to use the algorithm outlined above and currently approved and in place by the UCLA Health System as the research team believes it to be a generalizable model that could be applied to other health systems.

Creating family units

An overall address field will be constructed from the data pull including the address, city, state, and zip code fields. Primary telephone number, patient ID of the guarantor and insurance member ID will be used as other variables in the process to create the family units. The following steps taken to create these family units is described below:

1. Start with a single entry in the contact data pull
2. Add any other entries with the same patient ID as any existing entry to the family
3. Add any other entries with the same address as any existing entry to the family
4. Add any other entries with the same primary phone as any existing entry to the family
5. Add any other entries with a patient ID matching the patient ID of guarantor as any existing entry to the family
6. Add any other entries with the same insurance member ID as any existing entry to the family
7. Repeat steps 2-6 until no new matches are found - this forms a single family
8. Repeat steps 1-7 on the remaining entries to build each additional family until all entries have been associated with a family.

Please note - when there were errors with the address and telephone number, these variables were not used to group families (ex. instances with 20+ entries with the same data for telephone number).

Definition of active portal user:

We can only send portal R/R messages to patients who have signed up for the portal. Since some patients sign up for the portal but never use it, we define an active portal user as a patient (or proxy on behalf of the patient) who has used the portal within 12 months and who has logged in 1 or more times in the past 12 months (reference date for login activity will be selected by the research team and then working backwards by 365 days, excluding their initial activation login and any subsequent logins on the same date of account activation).

Selection of index patient from each family unit

For RCT2- One individual will be randomly selected as the index patient per family per stratum (e.g., if a single family contains eligible members in both the diabetic adult stratum and the nondiabetic younger adult stratum, one index patient will be selected for the former and another for the latter).

Selection of the index patient for primary analysis:

1. An active portal user per the definition above
2. The patient is affiliated with one of the primary care clinics of interest
3. The patient was randomly selected as the index patient in their family unit for one of the age group/diabetic groups

We will assess primary intervention effects among eligible index patients, and secondary analyses for the entire primary care registry since the impact of the intervention reflects the extent of portal penetration and high correlation that exists among members of the same family (up to 480,000 patients for RCT #2, (ISS-generated data extraction: of 430,000; IP-generated data extraction of approximately 50,000 patients meeting the SUPREME criteria for diabetes (MRNS only shared with the study team by the IP group).

Exclusion criteria

Patients will be excluded from the overall study if they are not part of UCLA's primary care registry per the above algorithm detailed in the inclusion criteria.

MEASURES

Dependent Measures

Vaccine Outcome: The primary outcome is influenza vaccination during the vaccination season as measured by analysis of EHR data. For children <9y who had not received prior influenza vaccination, the outcome will be at least 1 influenza vaccination.

Process Outcomes: These will include: (a) total # visits to the practice during the study time period, (b) # flu vaccine or nurse visits, and (c) missed opportunities. Visits will be measured by the EHR, using ICD-10/CPT codes to classify visits to primary care as preventive, acute/chronic, or nurse-vaccination. Missed opportunities are defined as # vaccine-eligible visits during which the patient did not receive an influenza vaccination. These

process metrics will help assess how the intervention worked.

Cost and Cost Effectiveness

Costs: Since the intervention is implemented centrally, we assume no added practice costs. We also assume practice costs/vaccination from portal R/R is identical to standard practice costs/vaccination. We will assess the time and costs of study and implementation personnel and non-personnel costs, distinguishing planning costs from intervention costs. We will measure costs using a standardized time study/resource survey sent weekly to all individuals working on the study that delineates (a) the # hours spent for each individual, and (b) research vs implementation time. We will use national salary estimates by work code from the Bureau of Labor Statistics to value personnel time in standard rates. We will measure non-personnel costs EHR hardware, software, materials.

We will assume that the actual per-dose vaccination costs (administration costs, vaccine costs, storage, etc.) are identical for intervention and comparison patients and equal to the average national reimbursement for an influenza vaccine dose. The difference in total costs between the study arms will be influenced by the total costs of implementing the intervention, the difference in vaccination rates within study arms, and the subsequent health care utilization by the population (which we can model from prior studies)

Effectiveness: For each RCT we will estimate effectiveness using model-based, standardized expected values (mean) at the end of each RCT. We will calculate incremental cost-effectiveness ratios (ICERs) for each intervention arm.

CONSENT PROCESS AND HIPAA AUTHORIZATION

We are seeking a Waiver of Informed Consent for the study. The study poses no more than minimal risk. The research could not practicably be carried out without a waiver of consent because:

It would not be possible to contact all of the participants associated with data or specimens to obtain consent.

The size of the potential study population is so large that it would not be feasible to obtain consent.

Requiring informed consent may introduce systematic bias into the data.

Requiring consent would introduce systematic bias into each of the RCTs. If patients know these studies will occur, it could influence their behavior in getting the flu vaccine prior to actual initiation of the study. Self-selection prior to the study of who would opt in or out would also bias the results as those who opt in may be more health conscious. This would in turn bias the results and the research team would be limited in the types of generalizable conclusions to be made.

For children, we request to waive both Parental Permission and Assent.

We are requesting a waiver of consent for the entire study so while there are no consent forms, the reminder recall messages will also be made available in Spanish when the portal technology has finished programming that capability.

As of now, no translated versions of the reminders are available as the programming of this translation functionality is still occurring on the technical side of the patient portal but will be uploaded for approval prior to use. No Spanish versions will be available as the current technology available with the portal only allows for single language - English.

HIPAA Authorization:

We are seeking a total Waiver of HIPAA Authorization for the entire study. We assure the PHI collected for this study from the UC records will not be reused or disclosed except as indicated in this application.

The investigators agree to the following:

- The protected health information requested is the minimum necessary to meet the research objectives
- The protected health information that is obtained as part of this study will not be used or disclosed to any other person other than study personnel or to the parties listed in item Section 17.1/item 2, except as required by law.

- Study Sponsors will not be provided with personal identifying information (including PHI) to take from the study site at any time, including the end of the study.
- Data and specimens shared with outside entities, such as study sponsors, will be coded or de-identified.

The Waiver is necessary and the research could not be practicably conducted without access to and use of the protected health information because the PHI is needed to identify potential participants' diabetic status (prior to randomization) and influenza vaccination status throughout the study. It would also not be feasible to individually contact the large number of potential subjects in the study.

PRIVACY AND CONFIDENTIALITY

This proposal for multiple RCTs involves reminding patients within the UCLA health system, via their patient portal, that they are due for an annual flu vaccine. Since the messages will all be delivered via the portal, patients must have their own unique ID and passwords to sign in, helping to maintain their privacy. Also, patients will sign on at a time and place convenient to them, ensuring that they can use a private (usually home) setting.

To maintain privacy we will carry out the following measures:

RCT 2: Patients in the intervention arms of the RCT will receive up to 4 reminders via the portal, notifying them of a new letter from their provider in the portal system. The letter will include the first name of the patient and the patient's provider name will be added below the signature line. The letter is only accessible to patients once they or their patient proxy (in the case of a patient proxy, typically for young children or elderly patients) log into their UCLA patient portal (password protected). The patient population that received a generic message in RCT #1 is being subdivided into 4 groups (children <18 years, young adults (18-<65 years), older adults (65+ years) and patients with diabetes meeting the SUPREME criteria. A message will only be sent after a child turns 6 months of age (the recommended minimum age for influenza vaccination).

Confidentiality will be maintained with the following procedures:

- 1) any data transfer will occur between entities at UCLA and will involve encrypted mechanisms
- 2) all electronic data will be stored in locked and password protected computers, in locked rooms. Only the statistician will have access to identifiable data.
- 3) All UCLA personnel will complete required CITI and HIPAA courses and training, and all personnel from other institutions will also be required to complete analogous courses and training. Verification of the completion of these trainings must be provided to UCLA personnel upon request.

RISKS TO SUBJECTS

The major risk is one of breach of privacy and confidentiality. We will maintain the strictest of procedures to prevent either of these problems as described above (i.e., staff training, maintaining strict confidentiality of data).

There is always a risk of complications with vaccination, but this study does not vaccinate patients per se -- rather, it reminds patients (or parents of eligible minors) to receive a recommended vaccine and patients should discuss the benefits and risk of influenza and vaccination with their healthcare provider.

The study does not represent more than minimal risk. The objective is to encourage patients to schedule a visit to see their primary health care provider and to make an appointment to receive a recommended vaccine. The vaccine is recommended by the Advisory Committee of Immunization Practices (ACIP) for all individuals over the age of 6 months and older on an annual basis. Therefore, indicating a patient is due for an influenza vaccination does not represent sensitive information. In addition, the message will only be delivered and accessible via the patient portal which is username and password protected. The greatest risk is one of loss of confidentiality.

BENEFITS TO SUBJECTS

The benefit to the subject is reminders to receive a recommended vaccine that offers protection from influenza, which can be very serious and can require hospitalization or can lead to death in some cases.

The benefit to society would be a better understanding of effective R/R messages and modalities that could be scaled up nationally and disseminated to other health systems to increase influenza vaccination (improve individual and herd immunity). This is particularly important for the influenza vaccine as in today's current society many have decided to forgo essential and recommended vaccines for themselves and their children, thereby increasing their personal risk.

COSTS FOR PARTICIPATION

Subjects will not incur any financial obligations from participation in the study.

PAYMENT FOR PARTICIPATION

No payments will be received by subjects.

STATISTICS AND ANALYTIC PLAN

Primary Analysis

We hypothesize that patients receiving gain-framed or loss-framed portal R/R messages will have higher influenza vaccination rates than no R/R, and we hypothesize that patients receiving pre-commitment prompts will have higher influenza vaccination rates than no prompts. Primary outcomes (patient receipt of flu vaccine) are binary; our main explanatory variable will be an indicator for the receipt of any portal-based R/R or prompt.

The analysis will be based on a 3x2 factorial design, with evaluation of a reminder framing intervention (gain-frame v. loss-frame v. no reminder), and a pre-commitment prompt intervention (pre-commitment v. no pre-commitment). Analyses will be stratified into 4 patient cohorts: <18y, 18-64 non-diabetic, 65+ non-diabetic, and 18+ diabetic. The pediatric age group (<18y) will be analyzed separately.

We will employ intent-to-treat analyses using mixed effects log-binomial regression models with practice random effects, an approach recommended for RCTs in which the goal is to estimate the causal effects of interventions on individuals, adjusted for clustering of patients by practice. The primary model terms will be reminder arm (gain-frame v. loss-frame v. none), and pre-commitment arm (prompt v. no prompt). Models will adjust for the following patient characteristics: age, gender, race/ethnicity, primary language, primary payor, and prior receipt of influenza vaccines in the last two years. Evaluation of study hypotheses will be performed using model contrasts, and treatment effects will be reported in terms of risk ratios and 95% CIs. In the event of computational issues, we will replace the log-binomial specification with a log-Poisson specification, and use model-robust standard errors for inference on treatment effect risk ratios.

Additional Analysis

Additional analyses will include evaluation of process measures (e.g., missed opportunities), evaluation of effect modification by patient characteristics, comparison of the gain-frame and loss-frame arms, and evaluation of vaccination receipt including self-reported vaccinations. Process measures will be analyzed similarly to the primary outcome but using different distributions and link functions as appropriate (e.g., negative binomial distributions for number of missed opportunities). Effect heterogeneity will be evaluated by introducing interaction terms into the primary model specification. All secondary analyses will use a significance level of 0.05. All analyses will be performed using SAS v. 9.4 (SAS Institute Inc., Cary, NC).

Process measures: We assessed the percentage of patients who opened the portal reminder letter, as well as the source of influenza vaccination data (health system within UCLA practices, external source via data transfer, patient/proxy update through normal portal processes, or patient/proxy update in response to portal reminders).

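### As written, the guarantor step of the family algorithm links in one direction only, so families joined only by guarantor can be split and their parts randomised to different arms

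*Combined protocol and SAP*

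**What the plan says.** The combined protocol and SAP builds families in the section Creating family units. Step 1 is "Start with a single entry in the contact data pull", with no rule on which entry comes first. Step 2 matches on patient ID. Steps 3, 4 and 6 each compare one field with itself:

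- Step 3: "Add any other entries with the same address as any existing entry to the family"
- Step 4: "Add any other entries with the same primary phone as any existing entry to the family"
- Step 6: "Add any other entries with the same insurance member ID as any existing entry to the family"

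Step 5, on the guarantor, compares two different fields: "Add any other entries with a patient ID matching the patient ID of guarantor as any existing entry to the family". Step 7 closes the family: "Repeat steps 2-6 until no new matches are found - this forms a single family". Step 8 moves on: "Repeat steps 1-7 on the remaining entries to build each additional family until all entries have been associated with a family". A note after the steps says that erroneous addresses and telephone numbers were not used for grouping.

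Under Specific Aims, "families will be randomized using a 3x2 factorial allocation", and one index member is taken per family per cohort; the index-patient section repeats that rule. Under Subject Population, the guarantor's ID is listed with address, phone and insurance ID as a field that family members have in common.

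**The concern.** Every other link is symmetric, so the starting entry cannot matter. The guarantor link is not. It runs from dependant to guarantor, never from guarantor to dependant, and it does not join two people who name the same guarantor. Step 7 only repeats the one-way rule, and step 8 works on unassigned entries, so a split is not repaired. This does not deliver the shared-field grouping described under Subject Population.

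Two things are at stake. First, one real family can supply two index patients in the same cohort, for example two siblings under 18, against the plan's own rule. Second, the parts are treated as separate families and can be allocated to different arms. The protocol recognises proxy portal use, typically for young children, so one adult could see a reminder for one child while a sibling counts as a no-reminder control. That would pull the contrast towards no effect.

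**Working it through.** The plan gives no family count or other figure on this point, so there is nothing to reproduce. The check applies steps 1 to 8 as written, in every processing order, to families whose only link is the guarantor: a guarantor G and dependants D1, D2 and so on.

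**Splits as written**

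- *G and D1.* Start at D1: {D1, G}, whole. Start at G: {G}, {D1}. Split in 1 of 2 orders.
- *G, D1 and D2.* Start at G (2 orders): {G}, {D1}, {D2}. Start at a dependant (4 orders): that dependant with G, the other alone. Split in 6 of 6; mean number of parts (2×3 + 4×2)/6 = 2.33.
- *G and three dependants.* Split in 24 of 24; mean (6×4 + 18×3)/24 = 3.25 parts.
- *Two dependants, G not in the data pull.* Split in 2 of 2.
- *Any of the families with G in the pull, with a valid shared address.* Split in none.

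So the starting entry decides whether a guarantor-dependant pair splits. With two or more dependants it decides only how.

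**Chance that the parts are allocated differently.** Assume equal allocation (1:1:1 for reminders is not stated) and independent randomisation of f parts. The chance that they are not all alike is 1 − (1/6)^(f−1) over the six cells and 1 − (1/3)^(f−1) over reminder arms. For f = 2 this is 5/6 = 0.833 and 2/3 = 0.667. Averaged over processing orders:

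| Family | Not all in one cell | Not all in one reminder arm |
|---|---|---|
| G + 1 | 1/2 × 0.833 = 0.417 | 1/2 × 0.667 = 0.333 |
| G + 2 | 1/3 × 0.972 + 2/3 × 0.833 = 0.880 | 1/3 × 0.889 + 2/3 × 0.667 = 0.741 |
| G + 3 | 1/4 × 0.995 + 3/4 × 0.972 = 0.978 | 1/4 × 0.963 + 3/4 × 0.889 = 0.907 |

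**Possible dilution.** The exposed share is not in the documents; take 1% to 5% of index patients as an assumption. As a worst case, let a reminder to one part act in full on a no-reminder relative. A control in a two-part family has a reminded relative with probability 2/3, and in a three-part family with probability 1 − (1/3)² = 8/9. The reminder-versus-none difference then shrinks by between 0.01 × 2/3 = 0.7% and 0.05 × 8/9 = 4.4% of its size. Real carry-over would be less than full.

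**Does the corrected rule work?** Matching patient ID or guarantor ID against either ID of an existing entry gave no splits in any order or configuration tested. Half-measures do not suffice. A two-way link alone still separates two dependants of an absent guarantor (2 of 2). A same-guarantor link alone always separates a guarantor whose own guarantor field is blank.

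**The case against.** Step 5 is garbled. Its ending follows the pattern of the symmetric steps, and Subject Population treats guarantor ID like the other shared fields. A symmetric match may be what was meant and what was coded. This stands: the documents establish a defect in the written rule, not in the families actually built.

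The counts above isolate one of several links. Most relatives may well share an address, phone or insurance ID, and then nothing splits. This also stands, and it limits the point to a subset of unknown size. Families whose address or phone was set aside as erroneous are the likeliest members.

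A guarantor has a billing role, and nothing says that this person is the portal proxy, or that one proxy serves both children. Contamination is therefore possible but not shown.

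A reader might infer that, because the primary model has practice random effects and no family term, split siblings in one cohort would make its tests anti-conservative. They would not. Within-family correlation inflates the error of a treatment contrast when relatives share an assignment, and separate fragments are assigned independently. In a simulation with 1,000 sibling pairs, two arms, no effect and an assumed intraclass correlation of 0.6, a test ignoring family rejected in 4.7% of trials when siblings were randomised independently and in 11.6% when randomised together. A second simulation at the same correlation gave 5.4% and 12.3%. A split parent and child would normally sit in different cohorts, which are analysed separately.

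Finally, Methods and Study Procedures speaks of patients, not families, being randomised. That wording needs reconciling with Specific Aims, but the one-index-per-family rule is affected under either.

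**Conclusion.** The point holds as a minor, correctable fault in a stated rule. Read literally, step 5 can split families held together only by guarantor, and always does so when two or more dependants depend on that link. The consequences are a breach of the one-index-per-family-per-cohort rule and possible cross-arm contamination towards no effect. The documents do not support a claim of inflated type I error, of widespread family splitting, or that the families used were in fact wrong. The effect on the primary result is probably small: even with full carry-over, an assumed exposed share of 1% to 5% dilutes the reminder effect by at most about 4.4% of its size in the cases worked. This rests on the literal reading of step 5, on family-level randomisation with equal allocation, and on that assumed share.

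**What to change.** If randomisation has not been done, reword step 5 so that an entry joins when its patient ID or guarantor ID equals the patient ID or guarantor ID of any entry already in the family, and confirm that the linkage program does this. Keep blank, placeholder or evidently erroneous guarantor IDs out of the match, in the spirit of the existing note on address and phone. The count of 20 or more in that note is only an example for telephone numbers, so any threshold for guarantor IDs has to be chosen and stated; a similar screen on insurance IDs is optional.

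The section's partly past tense suggests that families may already exist. If they are built and randomised, do not re-link. Correct the text to match the code, and report how many families and index patients would change under the symmetric rule. Refit the primary models without the index patients from those families. That exclusion uses only identifiers fixed before randomisation, so it does not disturb the comparison.

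Cost before randomisation: a short change to protocol and program and one rerun, with slightly larger families, marginally fewer index patients and a small risk of merging unrelated people. Afterwards: one count and one extra model fit per cohort.
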